#### **2.2.2.1.1 TSC-related Epilepsy**

Study 1042-TSC-2001 and Study 1042-TSC-3001 are parent studies for this OLE.

- In the single arm Phase 2 Study 1042-TSC-2001, the primary objective was to assess the preliminary safety and efficacy of GNX as adjunctive therapy for the treatment of seizures in participants aged 2 to 65 years with genetically or clinically confirmed TSC-related epilepsy. The core phase of the study (Part A) consisted of a 4-week baseline followed by a treatment phase, consisting of a 4-week titration and 8-week maintenance period. The primary efficacy endpoint was the percent reduction in countable TSC-associated seizures from the baseline through the end of the Period A treatment phase.
  - Review of data for the primary endpoint showed a median 16.6% reduction in 28-day primary endpoint seizure frequency relative to the 4-week baseline period, with 30.4% of patients achieving a 50% or more seizure reduction. The clinical study report (CSR) for the study was completed on 08 Mar 2023.

- In the double-blind Phase 3 Study 1042-TSC-3001, the primary objective is to assess the safety and efficacy of GNX compared to placebo as adjunctive therapy for seizures associated with TSC-related epilepsy in participants aged 1 through 65 years. The study consists of a 4-week baseline followed by a 16-week treatment phase, consisting of a 4-week titration and 12-week maintenance period.
  - Study 1042-TSC-3001 began enrolling in 2022 and is ongoing.

Additional information detailing ongoing and completed clinical GNX studies may be found in the current IB.

### **2.2.2.2 Clinical Safety Overview**

In all completed placebo-controlled studies, 63.5% (742/1168) of participants who received GNX and 51.9% (443/853) of participants who received placebo experienced at least 1 treatment-emergent adverse event (TEAE). In these studies, the most frequently reported (ie, in > 5% of participants) TEAEs in GNX-treated participants were: somnolence (23.84% GNX, 7.7% placebo), dizziness (12.2% GNX, 3.5% placebo), fatigue (11.2% GNX, 4.8% placebo), and headache (6.3% GNX, 6.9% placebo). All these events, except headache, occurred more frequently in GNX treated participants than placebo participants. CNS-related events appeared to be dose related, with the majority of these events occurring at doses  $\geq$  500 mg and were non-serious, mild to moderate in severity, and did not lead to discontinuation of treatment. These TEAEs were also anticipated based on the mechanism of action of GNX.

In all completed placebo-controlled studies, the incidence of serious adverse events (SAEs) was balanced between the GNX-treated participants (33/1168 participants, 2.8%) and placebo participants (26/853 participants, 3.0%), respectively. In these studies, the only SAEs reported in more than 1 participant in the GNX treatment group were seizure and sedation.

In all completed studies, including OL, long-term follow-up studies, 5.4% (118/2172 participants) of participants who received GNX experienced at least 1 SAE. With long-term exposure, no new safety findings were identified through the review of SAEs in these studies. The most frequently reported SAEs (ie, in > 2 participants) were seizure, SE, infantile spasms, epilepsy, pneumonia, pneumonia aspiration, pyrexia, , seizure cluster, dehydration, gastro-esophageal reflux disease, rash, somnolence, and upper respiratory tract infection. In all studies, most of the SAEs were considered unrelated to treatment according to the investigator, and most resolved.

The Phase 2 study (protocol 1042-TSC-2001) showed a consistent safety profile in a TSC population. Of the 24 participants screened, 4 discontinued the study due to adverse events (AEs), with somnolence, sedation, and fatigue being the most common treatment-emergent AEs. Additionally, 1 treatment-related SAE of seizure was reported.

Additional information describing the safety of GNX may be found in the current IB.

## **2.3 Benefit/Risk Assessment**

Based on clinical and non-clinical data from studies with GNX, the overall benefit/risk profile favors clinical development of GNX for the treatment of TSC-related epilepsy.

More detailed information about the known and expected benefits and risks and reasonably expected AEs of GNX may be found in the IB.

### **2.3.1 Risk Assessment**

CNS-related effects (such as somnolence, sedation, and gait disturbance) have been identified as an important risk related to the mechanism of action of GNX. In placebo-controlled studies, the most common CNS effects were somnolence, dizziness, fatigue, sedation, and gait disturbance. Of the AEs present at frequency > 1% and 2 times the frequency of placebo in the aggregate AE data, all 12 AEs are related to CNS function. The most common CNS-related AEs that led to discontinuation reported in placebo-controlled studies were dizziness (GNX 1.1%; placebo 0.4%); somnolence (GNX 0.9%; placebo 0.4%); and fatigue (GNX 0.8%; placebo 0.1%). These CNS effects were typically non-serious, mild to moderate in severity, and did not lead to discontinuation of treatment. However, in Study 1042-SE-2001, 2 SAEs of sedation were reported and led to early discontinuation and revision of the reference safety information.

The safety assessments to be performed in this study include vital signs, physical, neurological, and developmental examinations, 12-lead electrocardiogram (ECG), clinical laboratory tests, AE assessments, and Columbia Suicide Severity Rating Scale (C-SSRS). These are standard evaluations to ensure participant safety in this clinical study.

### **2.3.2 Benefit Assessment**

This is an OLE study to evaluate long-term safety and efficacy of adjunctive GNX therapy for seizures associated with TSC in children and adults. This patient population may benefit from the development of GNX as participants will receive GNX treatment that may help control their epilepsy.

### **2.3.3 Overall Benefit: Risk Conclusion**

Taking into account the measures to minimize risk to participants participating in this study, the potential risks identified in association with GNX are justified by the anticipated benefits to participants with TSC-related epilepsy.

### 3 OBJECTIVES AND ENDPOINTS

Objectives	
Primary Objective	

• To assess the long-term safety and tolerability of GNX as adjunctive therapy for seizures associated with TSC in children and adults.

	
Secondary Objectives	

• For the first year, to determine the percentage of change from baselinea in 28-day seizureb frequency during open-label treatment.

• For the first year, to assess the change in frequency of countable focal seizures frequency from baselinea during open-label treatment.

• For the first year, to assess changes in mood, behavior, and quality of life using SF-36.

• To assess overall clinical outcome using CGI-I scores by the clinician and the parent(s)/caregiver(s)/LAR(s).

• To evaluate the changes in seizure intensity and duration using the CGI-CSID.

	
Exploratory Objectives	

• To evaluate the long-term effects of GNX as add-on therapy to antiepileptic medications.

	
Endpoints	
Primary Endpoints	
The primary endpoints are the following safety endpoints:	

• Incidence and severity of AEs, SAEs and withdrawals and dose-reductions due to AEs.

• Vital sign measurements including blood pressure, heart rate, respiratory rate, body temperature, height, and body weight.

• Physical, neurological, and developmental examination.

• 12-lead ECG.

• Clinical laboratory tests.

• C-SSRS.

	
Secondary Endpoints	

• Percentage change from baselinea in 28-day seizureb frequency during open-label treatment (first year only).

• Percentage change from baselinea in 28-day seizureb frequency during the long-term treatment (first year only).

• Number (%) of participants considered treatment respondersc (first year only).

• CGI-I at the last scheduled study visit.

• Change from baseline in the quality-of-life scale SF-36 (first year only).

• Change from baselinea in the percentage of seizure-free days during treatment, based on seizure typeb (first year only).

• Change from baseline of CGI-CSID.

	

---

AE = adverse event; CGI-CSID = Clinical Global Impression of Change in Seizure Intensity/Duration; CGI-I = Clinical Global Impression of Improvement; C-SSRS = Columbia Suicide Severity Rating Scale; ECG = electrocardiogram; GNX = ganaxolone; PK = pharmacokinetic(s); SAE = serious adverse events; SF-36 = Short Form 36 (version 2); SQS = Sleep Quality Scale; TSC = Tuberous Sclerosis Complex.

- a Baseline for efficacy assessments is defined as based on the participant's prior study as follows:
  - Study 1042-TSC-2001 – the original baseline is considered to be Visit 2 for participants continuing in Study 1042-TSC-3002.
  - Study 1042-TSC-3001 – the original baseline is considered to be Visit 2 for participants previously randomized to GNX.
- Note: For other assessments, the baseline is considered to be Visit 1, the first visit of the OLE.
- b Seizure types are defined as the following: focal motor seizures without impairment of consciousness or awareness, focal seizures with impairment of consciousness or awareness with motor features, focal seizures evolving to bilateral, tonic-clonic convulsive seizures, and generalized motor seizures including tonic-clonic, bilateral tonic, bilateral clonic, or atonic/drop seizures. Seizures must have a motor component sufficiently prominent and distinct to clearly establish the observed symptoms as epileptic in origin. Seizures that do not count towards the efficacy endpoints include focal or generalized nonmotor seizures (eg, absence seizures or focal nonmotor seizures with or without impairment of awareness), infantile or epileptic spasms, and myoclonic seizures.
- c Treatment responders are defined as those participants with a  $\geq 50\%$  reduction from baseline in seizure frequency during open-label treatment.

## 4 STUDY DESIGN

### 4.1 Overall Design

This is a Phase 3, global, OLE study of adjunctive GNX treatment in children and adults with TSC-related epilepsy who previously participated in either Study 1042-TSC-3001 or Study 1042-TSC-2001. For this protocol, the term children will refer to the full range of pediatric participants.

For all participants who enter the OLE, the last visit in the parent Study 1042-TSC-3001 or Study 1042-TSC-2001 will be the same as the First Visit in this OLE study and visit activities will not be duplicated.

Procedures specific to this protocol and not otherwise considered standard of care, will not be performed until written informed consent/assent from the participant or their parent(s)/LAR(s), as appropriate, has been appropriately obtained.

Participants or their parent(s)/caregiver(s)/LAR(s) are expected to complete electronic seizure diary (eDiary) entries to document the number and type(s) of seizures daily throughout the first year of the study. After the first year, study assessments will focus on safety evaluation.

Caregiver and clinician global impressions of improvement will continue to be assessed to ensure that participants are continuing to receive benefit from treatment. A variety of clinician and caregiver administered outcome measures will be used at the study visits to assess efficacy. These include:

- Clinical Global Impression of Improvement (CGI-I) by parent(s)/caregiver(s) and clinician.
- Caregiver Global Impression of Change in Seizure Intensity/Duration (CGI-CSID).

- Short Form 36 (SF-36) (first year of the study only).

Safety monitoring assessments will be conducted throughout the study.

The maximum dose for all participants is 1800 mg/day.

Participants who discontinue the investigational product (IP) should undergo a 2-week taper period. The taper period may be shortened, if necessary, for participant safety. Participants who discontinue the IP before the scheduled completion of the study will have an Early Termination Visit, as per Visit 13 (Week 156), and return to the site 2 weeks after the end of the taper period to complete the safety follow-up assessments.

The study design is presented in Figure 1.

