## SUMMARY OF CHANGES FROM PREVIOUS VERSION

Protocol Amendments		
Summary of Changes Since Last Version of Approved Protocol		
Amendment Number	Amendment Date	Global/Country/ Site-Specific
3	19 Apr 2023	Global
Rationale for the Amendment		
The following changes are made in this global protocol amendment from version 3.0 to version 4.0 to:		

Reflect changes to the maximum overall study duration from 1 year to 3 years.

Include updated information regarding completed and ongoing clinical studies.

Add details on pregnancy testing.

		
Description of Changes		Section(s) Affected by Change
Minor editorial updates throughout for administrative changes, grammar, consistency, and clarity.		Throughout the document
Updated Protocol amendment date and version.		Protocol header, Title page, and Sponsor Signatory page
Applied a correction to the Protocol Title on the signatory pages; “Trial” corrected to “Study”		Sponsor Signatory page and Investigator Agreement page
The estimated duration of the study was updated from 1 year to 3 years.		Section 1.1, Section 1.3, Section 4.1.1, and Section 6.2.
Updated rationale text to clarify the completion of Study 1042-TSC-2001 and added summary text for the ongoing Study 1042-TSC-3001.		Section 1.1 and Section 2.2.2.1.1
Updated secondary objectives and endpoints to specify objectives and endpoints which are only to be assessed in Year 1.		Section 1.1, Section 3, and Section 9.2.3
Added text to clarify that seizure eDiaries will be completed in Year 1 of the study only.		Section 1.1, Section 4.1, Section 6.5, and Section 6.6.1
Added text to clarify that after Year 1, study assessments will focus on safety evaluation and that caregiver and clinician impressions of improvement will continue to ensure continued treatment benefit.		Section 1.1, and Section 4.1
Updated text to align with the Visit numbers and dates in the revised Schedule of Activities (SoA) for inclusion of Years 2 and 3, including references to the Early Termination Visit and End of Study definition.		Section 1.1, Section 4.1, Section 4.4, Section 7.1, Section 7.2, Section 8.1.2, Section 8.1.3, Section 8.2.2, Section 8.2.3, Section 8.3.1, Section 8.3.2, Section 8.3.3, Section 8.3.4, and Section 8.3.5

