### 1.3 Schedule of Activities

**Table 1. Schedule of Activities for Open-Label Phase**

Week (All dates are relative to the first OLE dose on Day 1)	0	Open-Label Maintenance												Safety Follow-up	
		Year 1				Year 2				Year 3 b					
		13	26	39	52	65	78	91	104	117	130	143	156		
Visit and Visit Windows (Telehealth permitted where it is accepted as the standard of care)	First Visit of the OLE a V1	All windows for these visits are $\pm$ 14 days												$\pm$ 3 days	
		V2 Phone	V3	V4 Phone	V5	V6 Phone	V7	V8 Phone	V9	V10 Phone	V11	V12 Phone	V13 or ET c		
Screening and Diagnosis															
Informed Consent/Assent	X														
Inclusion/Exclusion Criteria	X														
Demographics and Medical History Review d	X														
Safety Assessments															
Vital signs (BP, HR, RR, body temperature, height, weight)	X		X		X		X		X		X		X	X	
Physical/Neurological/Developmental Examination	X		X		X		X		X		X		X	X	
12-lead ECG	X		X											X	
Clinical Laboratory Tests e	X		X		X		X		X		X		X		
Pregnancy Test (and dispense pregnancy test for monthly home testing; WOCBP) f	X														
Investigational Product PK g	X		X		X										
Concomitant ASM Level Review (if collected per standard of care) h	X		X		X		X		X		X		X		
Adverse Events	X	X	X	X	X	X	X	X	X	X	X	X	X	X	
Concomitant Medication Review	X	X	X	X	X	X	X	X	X	X	X	X	X	X	
C-SSRS (since previous visit) i	X		X		X		X		X		X		X	X	

Week (All dates are relative to the first OLE dose on Day 1)	0	Open-Label Maintenance											Safety Follow-up
		Year 1				Year 2				Year 3 b			
		13	26	39	52	65	78	91	104	117	130	143	156
Visit and Visit Windows (Telehealth permitted where it is accepted as the standard of care)	First Visit of the OLE a V1	All windows for these visits are $\pm$ 14 days											$\pm$ 3 days
		V2 Phone	V3	V4 Phone	V5	V6 Phone	V7	V8 Phone	V9	V10 Phone	V11	V12 Phone	V13 or ET c
Efficacy Assessments													
Seizure eDiary review	X	X	X	X	X								
CGI-CSID	X		X		X		X		X		X		X
CGI-I by parents/ caregiver(s)/LAR(s) and clinician	X		X		X		X		X		X		X
SF-36	X		X		X								
Investigational Product													
Dispense IP	X		X		X		X		X		X		X

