### **8.2.4 Short Form 36**

The SF-36 is a multi-purpose survey designed to capture participant or parent(s)/caregiver(s)/LAR(s) perceptions of own health and well-being. The SF-36 has 36 items grouped in 8 dimensions: physical functioning, physical and emotional limitations, social functioning, bodily pain, general, and mental health. Version 2 of SF-36 will be used for this study (Section 10.10).

The SF-36 will be conducted at Visit 1 (First Visit of the OLE), Visit 3 (Week 26), and Visit 5 (Week 52).

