## 1. INTRODUCTION

This is a Phase 3, global, open-label extension (OLE) study and all participants will receive treatment with GNX after completing Study 1042-TSC-3001 (in this study participants previously randomized to placebo will be titrated to GNX under double-blind conditions prior to study completion) or Study 1042 TSC 2001. In both parent studies, GNX is to be titrated to a maximum dose of 1800 mg/day and given as an oral suspension (50 mg/mL) with food. Participants will continue the GNX dose determined in Study 1042-TSC-3001 or Study 1042-TSC-2001 in this OLE unless a dose change is clinically indicated. Participants who discontinue the IP should undergo a 2-week taper period, which may be shortened, if necessary, for patient safety. Participants who discontinue the IP before the scheduled completion of the study will have an Early Termination Visit, as per Visit 5 (Week 52), and also return to the site 2 weeks after the end of the taper period to complete the safety follow-up assessments. It is estimated that the maximum duration of participation in this study will be approximately 3 years. The purpose of this Statistical Analysis Plan (SAP) is to define the methodology for analyzing and summarizing the data collected during the conduct of Study 1042-TSC-3002.

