## **2. STUDY INFORMATION, OBJECTIVES, AND ENDPOINTS**

### **2.1. Protocol and Case Report Form Version**

This SAP is based on 1042-TSC-3002 Protocol Amendment 3 v4.0 dated 19APR2023 and case report forms (CRFs) v6.0 dated 12Sep2024. Unless superseded by an amendment, this SAP will be effective for all subsequent Protocol amendments and CRF versions.

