#### **4.5. Handling of Missing Data**

Available data from patients who withdraw from the study prematurely will be included in analyses, unless otherwise indicated. Summary statistics will be reported based upon observed data. No data will be imputed or carried forward for missing values or for patients who discontinue early. All missing data and missing or partial dates for AEs and medications will be queried for a value. In the unlikely event that no value can be obtained, substitutions will be made as described below.

- Missing and Partial Start/Stop Dates - AEs and Concomitant Medications**

The handling of partial start and stop dates for AEs are described in

**Table 4** below. Similar algorithms for handling missing and partial dates of concomitant medication usage are described in **Table 5**. In both cases, if a stop date is complete and an imputed start date is after the stop date, the start date will be set to the stop date.

- **Missing Seizure/Medication Diary Entries**

The calculation of seizure frequency endpoints will include only days for which diary entries are available. Missing seizure data will not be imputed.

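### The protocol's Early Termination visit (Visit 13) omits the SF-36 while the SAP's (Visit 5) includes it, so under the protocol Year-1 dropouts have no exit SF-36

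*Protocol*

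**What the plan says.** **Early Termination, protocol.** Section 4.1 says that a participant who stops study drug early "will have an Early Termination Visit, as per Visit 13 (Week 156"). The Synopsis and Sections 7.1 and 7.2 say the same, and Table 1 has one shared column for Visit 13 and Early Termination. The Amendment 3 change log, which records the extension from 1 to 3 years, lists the revised visit numbering, "including references to the Early Termination Visit and End of Study definition".

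**Early Termination, SAP.** SAP section 1 says that such a participant "will have an Early Termination Visit, as per Visit 5 (Week 52"). SAP 2.1 nevertheless states that the plan is based on "1042-TSC-3002 Protocol Amendment 3 v4.0 dated 19APR2023", the version that uses Visit 13.

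**SF-36.** Protocol 8.2.4: "The SF-36 will be conducted at Visit 1 (First Visit of the OLE), Visit 3 (Week 26), and Visit 5 (Week 52"). Table 1 agrees. It is the only instrument named in the first-year secondary objective on mood, behavior and quality of life.

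**Diary.** Participants or caregivers "document the number and type(s) of seizures daily throughout the first year of the study" (Protocol 4.1). The Table 1 row "Seizure eDiary review" is marked at Visits 1 to 5 and not in the Visit 13/Early Termination column.

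**Missing data.** SAP 4.5: "No data will be imputed or carried forward for missing values or for patients who discontinue early". SAP 5.2 limits efficacy analyses to scheduled visits and sends unscheduled data to listings. SAP 4.4.4 covers SF-36 scoring only. It names no analysis visit and does not mention an Early Termination value.

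**The concern.** SF-36 change is a first-year endpoint, but the exit visit is modelled on a Year-3 visit from which the first-year instruments have been dropped. A participant who stops at Week 20 attends an Early Termination visit and is rated on CGI-I and CGI-CSID, but is not given the SF-36. Week 13 is a phone visit without the SF-36, so that person leaves with a baseline and nothing after it. No reason for the omission is given, and the pattern fits an unintended effect of renumbering visits when the study was lengthened.

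Adverse events and lack of efficacy are both listed reasons for termination in Protocol 7.1, so those who leave may differ from those who stay. No later analysis can recover a questionnaire that was not given. The two documents also give different instructions on what is collected at exit, so the SAP may expect a value that sites following the protocol will not record.

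**Working it through.** The plan states no figure on this point: no power, effect size or Year-1 dropout rate. The check is a comparison of the schedules, followed by an illustration under assumed dropout.

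**Step 1. What a Year-1 dropout contributes under the protocol**

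| Endpoint | Source | Contribution |
|---|---|---|
| 28-day seizure frequency, responders | SAP 4.4.1, 4.4.2: seizures over days with diary data, × 28 | All diary days up to exit |
| Seizure-free days | SAP 4.4.5: proportion of days with diary data | All diary days up to exit |
| CGI-I, CGI-CSID | Protocol 8.2.2, 8.2.3: both include Visit 13 | Rated at exit |
| SF-36, leaving before Visit 3 (Week 26 ± 14 days) | Protocol 8.2.4 | No post-baseline value |
| SF-36, leaving between Visits 3 and 5 | Protocol 8.2.4 | Week 26 value only |

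The gap is therefore specific to the SF-36. SAP 4.5 includes the available data of early withdrawals, so their seizure data remain in the analysis.

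**Step 2. How many participants**

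Inputs: N = 169 (Protocol 9.4) or 150 (SAP 3.1). Assumed: Year-1 dropout d of 15%, 25% or 35%, at a constant hazard.

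- No exit SF-36: N × d.
- Leaving before Week 26, with no post-baseline SF-36: N × (1 − √(1 − d)).
- Leaving between Weeks 26 and 52, with Week 26 only: the difference.

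The share leaving before Week 26 is 1 − √0.85 = 0.078, 1 − √0.75 = 0.134 and 1 − √0.65 = 0.194.

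| N = 169 | d = 15% | d = 25% | d = 35% |
|---|---|---|---|
| No exit SF-36 | 25 | 42 | 59 |
| of whom no post-baseline SF-36 | 13 | 23 | 33 |
| of whom Week 26 only | 12 | 20 | 26 |

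(Rows are rounded separately.) With N = 150, 22.5 / 37.5 / 52.5 have no exit SF-36, of whom about 12 / 20 / 29 have no post-baseline value.

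**Step 3. What selection could do to the mean**

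If those who reach a visit have a mean change g points better than those who do not, the observed mean exceeds the all-participant mean by (share missing) × g. Taking g = 5 to 10 points, which is an assumption:

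| Visit | d = 15% | d = 25% | d = 35% |
|---|---|---|---|
| Week 26 (share 0.078 / 0.134 / 0.194) | 0.4 to 0.8 | 0.7 to 1.3 | 1.0 to 1.9 |
| Week 52 (share 0.15 / 0.25 / 0.35) | 0.75 to 1.5 | 1.25 to 2.5 | 1.75 to 3.5 |

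If g is zero there is no distortion. If g is negative the sign reverses.

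**Step 4. When the exit assessment takes place**

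Table 1 footnote c places the Early Termination visit before down-titration unless medically indicated, and Protocol 7.2 has the taper start at that visit. Protocol 8.1.2 has early leavers taper first and then undergo the Visit 13 assessments. An SF-36 added to this visit could therefore be completed on full dose or after the taper, depending on which passage a site follows.

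**The case against.** The case for leaving the schedule alone has real weight.

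- **Diary endpoints.** A reader might infer that Year-1 dropouts are lost from all first-year endpoints. The SAP derivations do not support that: the seizure endpoints use every available diary day and need no exit visit.
- **Diary checking.** A reader might infer that the last diary weeks go unreviewed. Protocol 6.5 and 8.2.1 have entries inspected for compliance, 10.1.7 has a monitor review all seizure entries and expects each within 48 hours, and 8.1.2 asks early leavers to keep the diary going during the taper. The missing mark in Table 1 is only a minor data-checking gap.
- **Completers only.** Those leaving after Visit 3 keep a Week 26 SF-36, so the SF-36 results are not confined to people who finish the year.
- **Bias toward benefit.** The SF-36 baseline is Visit 1 of the extension, when participants are already on ganaxolone, so change from that visit is not a clean estimate of benefit. The direction of any selection is plausible but not established.
- **Dropout rate.** Protocol 2.2.2.2 reports that 4 of 24 screened in Study 1042-TSC-2001 stopped for adverse events. That study included titration, whereas entrants here continue an established dose, so its rate does not carry over.
- **Importance.** The SF-36 is one descriptive secondary endpoint in an unpowered single-arm safety study, and CGI-I, which covers seizure control, behavior and tolerability, is collected at exit.

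All of this stands, and it narrows the point to the SF-36. It does not remove the conflict between protocol and SAP, and it does not supply the missing questionnaire.

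**Conclusion.** The point holds for the SF-36. The protocol's Early Termination visit has no SF-36, the SAP's does, and the SAP cites the same protocol version. Under the protocol, every Year-1 dropout lacks an exit SF-36, and those leaving before about Week 26 have no post-baseline value at all. With no imputation, SF-36 change at Week 26 and at Week 52 describes those who reached each visit.

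The size depends on dropout that the documents do not give. The counts of 25 / 42 / 59 without an exit value, and 13 / 23 / 33 of them without any post-baseline value, assume 15% / 25% / 35% Year-1 dropout of 169 and a constant hazard. The shifts in the mean rest on a further assumed gap between stayers and leavers and show scale only. The consequence is limited, but the change is worth making because it is cheap and the data cannot be recovered later.

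**What to change.** - **Protocol.** In Table 1 footnote c and Sections 4.1, 7.1, 7.2 and 8.2.4, state that an Early Termination visit on or before Week 52 also includes the SF-36 and a final eDiary review. Later Early Termination visits stay as Visit 13.
- **SAP section 1.** Align the description of Early Termination with the protocol.
- **SAP 4.4.4 and 5.2.** State that the Early Termination SF-36 counts as an analysis value despite the scheduled-visit restriction. Beside the Week 26 and Week 52 summaries, add a supplementary summary of change at Early Termination and at the last observed first-year assessment. Word it to be consistent with the no-carry-forward rule in SAP 4.5: it reports the last value observed and fills in no later visit.
- **Timing.** Reconcile Table 1 footnote c and Section 7.2 with Section 8.1.2 on whether the Early Termination assessments come before or after the taper, so that the exit SF-36 has one meaning. Which timing applies is for the sponsor to settle.

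Cost: a footnote and wording changes, one existing questionnaire and a diary check at a visit that already takes place (a few minutes each), and one extra table.
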